3.4 Eligibility Criteria

3.4.1 Informed Consent/Assent

A written informed consent form (ICF) and assent, as appropriate, will be freely obtained from the subject's parent or legal guardian, as applicable for local laws, in accordance with requirements of the trial center's institutional review board/independent ethics committee (IRB/IEC). The subject, as required by the trial center's IRB/IEC, must provide informed consent/assent at baseline, and as such must be able to understand that he or she can refuse entry into the trial, or withdraw from the trial at any time without justification, and there will be no consequences to their further care.

Age-appropriate assent documents will be created and subjects who are able will be required to re-consent or assent as appropriate if they matriculate from one age group to another. Subjects who became legal adults during the trial will be required to provide written informed consent as soon as they reach legal age.

Consent and assent will be documented on a written ICF and written informed assent form. The ICF/assent will be approved by the same IRB/IEC that approves this protocol. Each ICF/assent will comply with the International Conference on Harmonisation (ICH) Good Clinical Practice (GCP) Guideline²⁴ and local regulatory requirements. The investigator will review any written site-specific ICF/assent used in the trial, prior to submission to the IRB/IEC.

Investigators may discuss trial availability and the possibility for entry with a potential subject and his/her family without first obtaining consent and assent, as applicable. However, informed consent/assent (as applicable) must be obtained and documented prior to initiation of any procedures that are performed solely for the purpose of determining eligibility for this trial, including withdrawal from current medication(s).

Investigators may discuss this trial while the subject is still enrolled in the previous tolvaptan trial, however, consent and assent should not be obtained until the subject is ready to enroll into this trial at the baseline visit. All informed consent/assent procedures must be in accordance with the trial center’s IRB/IEC and local regulatory requirements.

Once appropriate essential information has been provided and fully explained in layman’s language to the subject and his/her parent or legal guardian by the investigator (or a qualified designee), and it has been documented that the subject and his/her parent or legal guardian has had the opportunity to ask questions, the IRB/IEC-approved written ICF/assent will be signed and dated by both the subject’s parent or legal guardian and the person obtaining consent (investigator or designee), as well as by any other parties required by the IRB/IEC. In addition, the subject, as required by the trial center’s IRB/IEC, must provide ICF/assent by signing the appropriate form. The subject’s parent or legal guardian will receive a copy of the signed ICF and assent form (as applicable); the originals shall be kept on file by the investigator.

Subjects’ parents or legal guardian(s) may be asked to sign additional ICFs if the protocol is amended to significantly add or change procedures. Subjects may be asked to re-assent as appropriate if the protocol is amended to significantly add or change procedures.

3.4.2 Inclusion Criteria

Subjects invited to participate in the core safety follow-up component of the trial must satisfy all ICF/assent requirements, as well as meet all the following inclusion criteria (Table 3.4.2-1):

1.	Enrollment in a previous tolvaptan pediatric trial for hyponatremia
2.	Trial-specific written informed consent/assent obtained from a parent/guardian or legally acceptable representative, as applicable for local laws, prior to the initiation of any protocol-required procedures. In addition, the subject must provide informed assent at baseline and must be able to understand that he or she can withdraw from the trial at any time
3.	Ability to comply with all requirements of the trial
4.	Willingness to be clinically followed for 6 months

Inclusion criteria for the optional tolvaptan treatment component are outlined in [Appendix 5](#).

3.4.3 Exclusion Criteria

There are no exclusion criteria for entry into the core safety follow-up component of this trial.

Exclusion criteria for the optional tolvaptan treatment component are outlined in [Appendix 5](#).

3.5 Outcome Variables

3.5.1 Primary Outcome Variable

Data for the primary efficacy variable will be collected for all subjects receiving tolvaptan in the optional tolvaptan treatment component of the trial, and will be summarized as follows:

- Change from baseline in serum sodium while tolvaptan is being administered

3.5.2 Secondary Outcome Variables

3.5.2.1 Efficacy Variables

Data for the secondary efficacy variables will be collected for all subjects receiving tolvaptan in the optional tolvaptan treatment component of the trial and will be summarized as follows:

- Percentage of subjects who require rescue therapy while on tolvaptan
- Percentage of subjects who have recurrence of hyponatremia while on tolvaptan
- Percentage of subjects requiring continuation of tolvaptan following 30 days of treatment

Additionally, for all subjects, the following variable will be assessed and summarized:

- Change from baseline in QoL assessments (monthly for subjects on tolvaptan)

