3.1.2 Optional Tolvaptan Treatment Component

Subjects enrolled in the 6-month core safety follow-up component may be eligible to receive optional tolvaptan treatment for their hyponatremia. Eligibility criteria for optional tolvaptan treatment are outlined in [Appendix 5](#). Eligibility for optional tolvaptan treatment must be determined at the pre-treatment baseline visit (Day -4 to Day -1) of each dosing cycle. Eligible subjects can be treated at any time with optional tolvaptan during the 6-month core safety follow-up component. Optional tolvaptan treatment duration will be case-specific; it can be short-term or long-term, and consist of 1 or more treatment cycles. When a cycle with optional tolvaptan treatment is completed, including the Follow-up Phase visits, subjects will continue in the core safety component to complete the remainder of visits until Month 6. Within this trial, tolvaptan treatment will not extend beyond the 6-month core safety trial period. If the subject completes the 6-month core safety component while on optional tolvaptan treatment, the subject will complete the Month 6 core safety component visit, terminate treatment, and immediately enter the Follow-up Phase.

If a subject simultaneously participates in both core safety and optional tolvaptan treatment components, the visit days will be calculated between both components to ensure the assessments can be overlapped, where applicable.

3.1.2.1 Treatment Interruption on Day 30

Thirty days after the start of optional tolvaptan treatment, subjects will interrupt treatment for up to 2 doses (Days 31-32). The need for continuing treatment after this tolvaptan interruption will be assessed at minimum once daily (or more as needed) during this time.

Subjects who are expected to receive tolvaptan for greater than 30 days duration should demonstrate the need for continued treatment by discontinuing tolvaptan for up to 2 consecutive doses while undergoing close monitoring of serum sodium levels.

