3.7.2 Optional Tolvaptan Treatment Component

If a subject has a clinical need for tolvaptan, the subject may be screened for eligibility to be treated with tolvaptan (see [Appendix 5](#)). To assess the subject's eligibility to receive tolvaptan, the subject must have been off treatment with IMP for 7 days following the end of treatment in the previous tolvaptan trial.

Subjects who meet the eligibility criteria for tolvaptan treatment will be administered tolvaptan based on age, weight, and the use of CYP3A4 inhibitors on Day 1 of the cycle. Subsequent dosing adjustments are based on serum sodium response. Refer to [Section 3.2.1.2](#) for dosing guidelines.

Trial assessments and time points for the optional tolvaptan treatment component are summarized in [Table 3.7.2-1](#) and described in [Section 3.7.3.2](#).

Table 3.7.2-1 Schedule of Assessments for Each Treatment Cycle																	
Procedures^a	Pre-treatment Baseline^b	Titration Phase^b			Post-titration						Treatment Cycle Month 2	Treatment Cycle Month 3+ (Maintenance)	Month 6 (D173) Cycle DC (+ 2 wk)	Follow-up Phase^k			
		Day 1	Day 2 and 3	Day 4	Day 7, 14 and 21	Day 30 (±1)	Day 31^c	Day 32^c	Day 33^c	Day 34^c				24 (±4) hours post-last dose	7 (±1) days post-last dose	14 (±2) days post-last dose	
	Days -4 to -1										every 2 weeks (±2 days) Mth 2 Wk 2 (D47), Mth 2 Wk 4 (D61)	Once monthly (±2 days) Mth 3 (D89), Mth 4 (D117), Mth 5 (D145)					
Review eligibility criteria for treatment	X																
Vital signs	X	X	X	X	X	X	X	X	X	X	X	X	X	X	X	X	
Physical examination ^d	X											X	X				
Body height and weight/ growth percentiles	X											X	X				
Pregnancy test ^e	X								X		X	X		X			
Clinical status assessment	X						X	X	X	X	X	X					
Neurological assessment ^f	X						X	X	X	X	X	X					
Quality of Life assessment	X											X					
Assess ALT, AST, BT, and creatinine	X					X					X ^g	X	X	X			
Assess serum sodium ^h	X	X	X	X	X	X	X	X	X	X	X	X	X	X	X	X	

- ^bTitration can be up to 4 days. Cycles can be repeated as needed during the 6-month core safety component. If a subject is off tolvaptan treatment for ≥ 72 hours, titration/reinitiation of tolvaptan will require reassessment of eligibility criteria and will begin in a hospital setting as part of a new treatment cycle.
- ^cDuring the Day 30 treatment interruption, Days 31, 32, 33 and 34 must follow consecutively. Once the Day 30 visit is determined, the subsequent visit days do not have a window.

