- 9) Body height and body weight will be measured.
- 10) Growth percentile will be calculated. Prior growth development information should also be collected, if available.

- 11) Tanner Staging will be transferred from the last assessments from the previous trial or completed as part of the physical examination, as appropriate. Historical staging information should also be collected, if available. A subject who has reached Stage 5 (both in pubic hair and genitalia) does not need to continue with Tanner Staging.
- 12) If the subject's last LFT (AST, ALT or BT) was abnormal or the subject's baseline visit occurred > 30 days after completion of the previous trial, the subject will be required to have LFTs assessed at baseline. If the subject's last LFTs were normal and the baseline visit occurred < 30 days after completion of the previous trial, LFTs will be collected at Month 1 or Month 2.
- 13) Quality of Life assessment will be performed, as appropriate by age and where available.
- 14) Concomitant medications will be recorded. If > 30 days have lapsed since the previous tolvaptan trial, medications taken within 30 days of enrollment will be recorded.
- 15) Adverse events will be assessed.

3.7.3.1.2 Months 1, 2, 3, 4, and 5

Subjects and/or their parents or legal guardians will be contacted by telephone at the end of Months 1, 2, 3, 4, and 5 (+ 2 weeks) to assess any new or ongoing AEs and to collect information on any medications administered since the last visit.

If the subject's last LFTs were normal and the baseline visit occurred < 30 days after completion of the previous trial, LFTs will be collected at Month 1 or Month 2 (in-clinic visit or local laboratory).

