3.7.3.2.1 Pretreatment Baseline Visit

The following procedures will be performed during the pretreatment baseline visit (Days -4 to -1) to ensure the subject qualifies for each tolvaptan treatment cycle:

- 1) Eligibility criteria (see [Appendix 5](#)) will be reviewed.
- 2) A clinical status assessment including a full neurological examination will be performed. If the subject has any positive findings on the clinical status assessment at the second or subsequent pretreatment baseline visits, a full neurological examination can be performed per investigator judgment.
- 3) Vital signs (blood pressure, heart rate, respiratory rate, and temperature) will be assessed at each visit after the subject has been supine for ≥ 3 minutes. Vital signs should be performed prior to the blood draws.
- 4) A full physical examination will be performed if it overlaps with the same assessment at the core safety baseline visit. Otherwise, a directed physical examination will be performed. Physical examination should include a fontanelle assessment as age appropriate.
- 5) Body height will be measured.
- 6) Body weight will be measured.
- 7) Growth percentile will be calculated.
- 8) A blood sample for ALT, AST, BT and creatinine will be collected.
- 9) A urine or serum pregnancy test will be performed on female subjects ≥ 12 years of age and female subjects < 12 years of age if menstruation has started.
- 10) Within 48 hours prior to tolvaptan administration, 2 samples for serum sodium testing will be collected at least 12 hours apart.
- 11) Quality of Life assessment will be performed, as appropriate by age and where available.
- 12) Concomitant medications will be recorded.
- 13) Adverse events will be assessed.

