The following assessments will be performed:

- 1) Vital signs (blood pressure, heart rate, respiratory rate, and temperature) will be assessed after the subject has been supine for ≥ 3 minutes. Vital signs should be assessed prior to blood draws.
- 2) A clinical status assessment will be performed. If the subject has any positive findings on the clinical status assessment, a full neurological examination can be performed per investigator judgment.
- 3) A blood sample will be collected for serum sodium testing at 24-hours (± 4 hours) post last dose (trough) with the results reviewed prior to a subsequent tolvaptan dose.
- 4) Tolvaptan will be administered.
- 5) Sufficient tolvaptan will be dispensed for subjects that are outpatients for QD dosing until their next scheduled visit. Subjects and their parents/legal guardians

will be instructed to return any remaining tolvaptan at the next visit for dose reconciliation.

- 6) Concomitant medications will be recorded.
- 7) Adverse events will be assessed.
- 8) Instruct subjects not to take a tolvaptan dose on the day of the next scheduled visit.

3.7.3.2.5 Treatment Cycle Month 2: Month 2 Week 2 and Month 2 Week 4 (± 2 days)

The next clinic visit should occur 2 weeks after the decision to continue treatment is made (Month 2 Week 2, Day 47 [± 2 days]), and then 2 weeks thereafter if treatment is continued (Month 2 Week 4, Day 61 [± 2 days]). Subjects should arrive to the clinic prior to taking the morning dose of tolvaptan.

The following assessments will be performed during each visit during the second month of each treatment cycle:

- 1) Vital signs (blood pressure, heart rate, respiratory rate, and temperature) will be assessed after the subject has been supine for ≥ 3 minutes. Vital signs should be assessed prior to blood draws.
- 2) A blood sample for serum sodium testing must be assessed at 24 (± 4) hours post-last dose (trough) with the results reviewed prior to subsequent tolvaptan dosing.
- 3) A blood sample for ALT, AST, BT and creatinine will be collected (Month 2 Week 4 visit only).
- 4) For each treatment cycle, a single PK blood sample will be collected after 8 consecutive weeks of tolvaptan dosing for the determination of tolvaptan and metabolites plasma concentrations.
- 5) A clinical status assessment will be performed. If the subject has any positive findings on the clinical status assessment, a full neurological examination can be performed per investigator judgment.

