3.7.3.2.6 Maintenance Phase

3.7.3.2.6.1 Treatment Cycle Month 3 (and every month thereafter) (±2 days)

Subjects will return to the clinical trial site for assessment once monthly for Month 3 (Day 89 [± 2 days]), Month 4 (Day 117 [± 2 days]), Month 5 (Day 145 [± 2 days]) and Month 6 (Day 173[± 2 days]). Subjects should arrive to the clinic prior to taking the morning dose of tolvaptan. The following procedures will be performed:

- 1) Vital signs (blood pressure, heart rate, respiratory rate, and temperature) will be assessed after the subject has been supine for ≥ 3 minutes. Vital signs should be assessed prior to blood draws.
- 2) A urine or serum pregnancy test will be performed at each visit on female subjects ≥ 12 years of age and female subjects < 12 years of age if menstruation has started (Months 3, 4, and 5).
- 3) A directed physical examination will be performed. Physical examination should include a fontanelle assessment as age appropriate.
- 4) Body height will be measured (Months 3, 4, and 5).
- 5) Body weight will be measured (Months 3, 4, and 5).
- 6) Growth percentile will be calculated (Months 3, 4, and 5).
- 7) A clinical status assessment will be performed. If the subject has any positive findings on the clinical status assessment, a full neurological examination can be performed per investigator judgment (Months 3, 4, and 5).
- 8) A blood sample for ALT, AST, BT, and creatinine will be collected.
- 9) A blood sample for serum sodium testing will be collected at 24 hours (± 4 hours) post-last dose (trough).
- 10) Tolvaptan dispensed the previous month will be returned for accountability.
- 11) Tolvaptan will be administered in the clinic (Months 3, 4, and 5).
- 12) Sufficient tolvaptan will be dispensed for subjects that are outpatients for QD dosing until their next scheduled visit. Subjects and their parents/legal guardians will be instructed to return any remaining tolvaptan at the next visit for dose reconciliation.
- 13) A single PK blood sample will be collected if missed at Month 2 and there have been 8 weeks of consecutive tolvaptan treatment.
- 14) Quality of Life assessments will be performed, as appropriate by age and where available (Months 3, 4, and 5).
- 15) Concomitant medications will be recorded.
- 16) Adverse events will be assessed.

- 17) Instruct subjects not to take a tolvaptan dose on the day of the next scheduled visit (Months 3, 4, and 5).

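### The QoL endpoint is defined as monthly on tolvaptan, but the treatment-cycle schedule has no QoL between pretreatment and Month 3 (Day 89 ± 2)

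*Protocol*

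**What the plan says.** The endpoint in Protocol Section 3.5.2.1 is "Change from baseline in QoL assessments (monthly for subjects on tolvaptan"). The Synopsis carries the same frequency.

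The schedule for a treatment cycle is in Table 3.7.2-1 and Section 3.7.3.2:

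- Pretreatment baseline, Days -4 to -1 (Section 3.7.3.2.1): "Quality of Life assessment will be performed, as appropriate by age and where available".
- Maintenance visits (Section 3.7.3.2.6.1): "Quality of Life assessments will be performed, as appropriate by age and where available (Months 3, 4, and 5"). These visits are held "once monthly for Month 3 (Day 89 [± 2 days"]) and then on Days 117 and 145.
- In Table 3.7.2-1, the row "Quality of Life assessment" is marked in two columns only, pretreatment baseline and Month 3+.

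The core component adds QoL at its own baseline visit and at Month 6/ET (Sections 3.7.3.1.1 and 3.7.3.1.3). Core Months 1 to 5 are telephone contacts "to assess any new or ongoing AEs and to collect information on any medications administered since the last visit".

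**The concern.** An endpoint that states a frequency needs a visit schedule that collects the data at that frequency. Here the first three months of a cycle contain no QoL measurement after the pretreatment form.

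That is the period in which a short course is completed, and short courses are an intended use. The Synopsis gives a few days of treatment for one episode as an example, and the objectives name repeated short-term treatment alongside chronic treatment. A gap of 72 hours or more starts a new cycle (Section 3.1.2.1), so the count towards Month 3 starts again. A child could accumulate more than 89 treated days over several cycles and still have no in-cycle, on-treatment QoL.

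At stake is whom the QoL result describes. The in-cycle values would come only from children who went on past the Day 30 interruption, or were excused from it, and were still on tolvaptan at about Day 89.

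**Working it through.** The plan gives no figure to reproduce, and no power or sample-size calculation bears on the point. The check sets the visit lists side by side and then counts.

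**Step 1: QoL at each roughly monthly point of a cycle**

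| Visit | Source | QoL listed? |
|---|---|---|
| Pretreatment, Days -4 to -1 | 3.7.3.2.1 | Yes |
| Day 30 | 3.7.3.2.4 | No |
| Month 2 Week 2, Day 47 | 3.7.3.2.5 | No |
| Month 2 Week 4, Day 61 | 3.7.3.2.5 | No |
| Months 3, 4, 5 (Days 89, 117, 145) | 3.7.3.2.6.1 | Yes |
| Cycle Month 6, Day 173 | 3.7.3.2.6.1 | No |
| Core Month 6/ET | 3.7.3.1.3 | Yes |

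For Month 2 the protocol sets out a full list ("The following assessments will be performed during each visit during the second month of each treatment cycle"), and QoL is not on it. The lists for Days 1 to 21 and for Days 31 to 34 have no QoL either.

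**Step 2: spacing**

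The Month 3, 4 and 5 visits are 117 − 89 = 28 and 145 − 117 = 28 days apart, so the monthly frequency holds from Month 3. The earliest in-cycle, on-treatment form is on Day 89 − 2 = 87. Of Days 30, 61, 89, 117 and 145, three of five carry QoL. For a child treated from near core entry to core Month 6, the core visit supplies one more, giving four of six.

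**Step 3: the core Month 6/ET exception**

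Treatment may begin on any day of the core period. For a child still on drug at its end, "the subject will complete the Month 6 core safety component visit, terminate treatment, and immediately enter the Follow-up Phase". The Month 6 QoL therefore precedes stopping. If core Month 6 falls on day M, the latest start that reaches cycle Day 89 is core day M − 89 + 1, which is day 92 for M = 180 and day 95 for M = 183. A child who starts later cannot reach the Month 3 visit, but has one on-treatment value if still dosing at core Month 6.

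**Step 4: illustration of how often no on-treatment QoL results**

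The documents give no distribution of start days or durations. Assume one continuous cycle, no early termination, and start days spread evenly over days 1 to M. A course of d days, with d below 89, has no on-treatment QoL when it ends before day M, that is, for start days 1 to M − d. The share is (M − d)/M.

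| Course d | M = 180 | M = 183 | Range, M = 168 to 197 |
|---|---|---|---|
| 30 days | 150/180 = 83% | 153/183 = 84% | 82% to 85% |
| 60 days | 120/180 = 67% | 123/183 = 67% | 64% to 70% |
| 88 days | 92/180 = 51% | 95/183 = 52% | 48% to 55% |

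The remaining start days give a single value, at core Month 6.

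**The case against.** Three counter-arguments deserve weight.

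1. *The endpoint can still be produced.* Section 3.5.2.1 introduces the QoL variable as one for all subjects. Protocol Section 7.4.2 and SAP Section 5.1.7.1 list it without a frequency. Change from core baseline to Month 6/ET is available for every child with a suitable form. This stands: what is not delivered is the stated frequency on tolvaptan, not the whole endpoint.
2. *Monthly may refer to the maintenance visits.* Table 3.7.2-1 labels the Month 3+ column as once monthly, and QoL is scheduled at every visit in that column. This is a possible reading, but neither the Synopsis nor Section 3.5.2.1 limits the variable to maintenance. Both apply it to subjects on tolvaptan without qualification.
3. *A form after a few days of dosing would say little.* The PedsQL versions used have a 7-day recall (Section 3.7.4.2), so such a form would largely describe the days before treatment. This stands for very short courses. It does not explain the absence of QoL at Day 30 or in Month 2.

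A reader might also infer that every course under 89 days yields no on-treatment QoL. The core Month 6/ET visit disproves that for a child still on drug then.

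**Conclusion.** The definition and the schedule disagree. Within a cycle, the monthly frequency is not met before Day 89 ± 2. A course that ends earlier has no on-treatment QoL unless the child is still on tolvaptan at core Month 6/ET. On the even-start illustration, that leaves about 83% to 84% of start days without any on-treatment value for a 30-day course, and about 51% to 52% for an 88-day course, with core Month 6 at day 180 to 183. Those shares rest on the assumptions in the working and are not predictions. The core schedule is taken from the visit lists in Section 3.7.3.1.

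On-treatment QoL would come mainly from long-term continuers. It is tempting to conclude that this favours tolvaptan, but the documents do not support a direction. Early stoppers may include children with adverse events or rescue therapy, and also children whose hyponatremia resolved, while those who continue have a persisting need. There is no comparator, and the analysis is descriptive. Nor do the documents say how many cycles would be short; they only permit short courses.

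SAP Section 5.1 states that no subject received optional tolvaptan. The inconsistency is in the plan and would matter if the design were reused; it does not affect reported results.

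**What to change.** Add the two PedsQL instruments to the Day 30 and Month 2 Week 4 visits in Table 3.7.2-1 and in Sections 3.7.3.2.4 and 3.7.3.2.5. On-treatment forms would then fall on Days 30, 61, 89, 117 and 145, at intervals of 31, 28, 28 and 28 days, which matches a monthly endpoint. Courses that end before Day 30 would still have no on-treatment form unless ongoing at core Month 6/ET, which is acceptable given the 7-day recall and should be stated.

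If the extra forms are not wanted, remove *monthly* from the Synopsis and Section 3.5.2.1, and state that on-treatment QoL describes only cycles that reach Month 3 or are still ongoing at core Month 6/ET.

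The cost of the first option is a small questionnaire burden (23 and 18 items) at two visits already held in clinic, plus edits to the schedule. The second is a wording change.
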